## **10.2 Concomitant medication**

Concomitant medications and non-drug therapies will be coded using World Health Organization Drug Dictionary (WHO-DD, the latest available version). Concomitant medications are medications taken at least once after the start of first study-drug administration. Medications stopped prior to the day of the start of first study-drug administration will not be considered concomitant medication. The prior medication will not be summarized, but they will be listed along with concomitant medications. Only concomitant medications will be summarized. Medications that started during the follow-up period will only be included in the follow-up concomitant summary table and will be flagged in the listing.

Individual data listings will be presented for each subject and summarized by WHO-DD Anatomical Therapeutic Chemical (ATC) anatomical group, and preferred term using frequency counts and percentages. Subjects who take the same medication more than once will be counted only once for that preferred term.

Dispensing of Nucleos(t)ide (NUC) will be listed for CHB cohorts, as appropriate.

### 10.3 Laboratory

#### 10.3.1 Definition of variables

##### Hematology Parameters

- Hemoglobin
- Red Blood Cell Count
- Hematocrit
- Mean Cell Volume (MCV)
- Mean Cell Hemoglobin (MCH)
- Mean Cell Hemoglobin Concentration (MCHC)
- Platelets
- White Blood Cell Count
- Neutrophils
- Lymphocytes
- Monocytes
- Eosinophils
- Basophils

##### Chemistry Parameters

- Sodium
- Potassium
- Chloride
- Bicarbonate
- Glucose
- Urea
- Creatinine (including calculated creatinine clearance)
- Creatine kinase
- Uric acid
- Phosphate
- Total calcium
- Anion gap
- Cholesterol
- Albumin
- Globulins
- Protein
- Total bilirubin
- Conjugated bilirubin
- Gamma glutamyltransferase (GGT)
- Alkaline phosphatase (ALP)
- Alanine aminotransferase (ALT)
- Aspartate transaminase (AST)
- Lactate dehydrogenase (LD)
- Triglycerides
- Amylase
- Lipase
- C-reactive protein
- Troponin I

##### Coagulation Parameters

- Partial Thromboplastin Time (PTT)
- Prothrombin Time (PT)
- INR

##### Urinalysis Parameters

- Leukocytes
- Nitrites
- Urobilinogen
- Protein
- pH
- Blood
- Specific Gravity
- Ketone
- Bilirubin
- Glucose

Microscopic urinalysis will be performed if indicated: White blood cells, red blood cells, epithelial cells, and bacteria.

### **10.3.2 Biostatistical methods**

All hematology, chemistry, coagulation and urinalysis parameters will be summarized using descriptive statistics for each dose level (cohort) for all time points assessed, including change from baseline (last pre-dose value) for all post-dose assessments. All continuous parameters will be summarized using the units reported from the laboratory.

Laboratory values will be compared to normal range of the single local laboratory and values that fall outside of the normal ranges will be flagged as: H (High) and L (Low) in the data listings. Results that were flagged as 'LP' will be reported as 'L' and results flagged as 'HP' will be reported 'H'. Shift tables from Day 1 (pre-dose) to all follow-up visits will also be generated for each hematology, chemistry and coagulation laboratory parameter with values of Within Normal Limits (WNL), High, and Low used for the shift categories.

To assess the liver function of CHB patients, number of subjects with ALT above the upper limit of normal over time will be summarized for CHB cohorts.

All laboratory data will be included in the by-subject data listings. Microscopic urinalysis will only be listed.

Time series of mean values for the following safety assessments will be plotted by NHV and CHB Cohorts.

- Creatinine
- Creatine Kinase
- AST
- ALT
- Total Bilirubin

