9. A family history of congenital long QT syndrome, Brugada syndrome or unexplained sudden cardiac death
10. Symptomatic heart failure (per NYHA guidelines), unstable angina, myocardial infarction, severe cardiovascular disease (ejection fraction < 20%, transient ischemic attack (TIA) or cerebrovascular accident (CVA) within 6 months prior to study entry
11. History of malignancy within the last 5 years except for adequately treated basal cell carcinoma, squamous cell skin cancer, superficial bladder tumors, or in situ cervical cancer. Participants with other curatively treated malignancies who have no evidence of metastatic disease and >1 year disease-free may be entered following approval by the Sponsor Medical Monitor
12. History of major surgery within 3 months of Screening
13. Regular use of alcohol within one month prior to the Screening visit (i.e., more than fourteen units of alcohol per week [1 Unit = 150 mL of wine, 360 mL of beer, or 45 mL of 40% alcohol])
14. Recent (within 3 months) use of illicit drugs (such as cocaine, phencyclidine [PCP], MDMA) or positive test for such drugs of abuse at screening. Subjects who are on prescription medications that cause a positive result on urine drug screen are eligible based on PI discretion. Subjects with a positive urine drug screen for opioids, cannabinoids or benzodiazepines may be eligible based on PI discretion.

15. Use of an investigational agent or device within 30 days prior to dosing or current participation in an investigational study
16. Has any clinically significant history or presence of poorly controlled or decompensated neurological, endocrine, cardiovascular, pulmonary, hematological, immunologic, psychiatric, metabolic, or other uncontrolled systemic disease, that may affect participation in the study
17. Any concomitant medical or psychiatric condition or social situation that would make it difficult to comply with protocol requirements or put the participant at additional safety risk
18. Has a history of coagulopathy (including deep vein thrombosis and pulmonary embolism) or stroke within 6 months of baseline, and/or concurrent anticoagulant medication(s).
19. Patients with any of the following laboratory abnormalities at screening:
 - a. Serum creatinine > 1.5 mg/dL (132.6 µmol/L)
 - b. International normalized ratio (INR) > 1.5 × ULN
 - c. Platelets < 70,000 cells per microliter
 - d. Hepatic transaminases (ALT or AST) > 5X ULN

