### 3. STATISTICAL CONSIDERATIONS

Data will be handled and processed according to the sponsor's representative (Novotech (Australia) Pty Ltd) Standard Operating Procedures (SOPs), which are written based on the principles of GCP.

All data collected on the eCRFs will be presented in the data listings and will be listed and sorted by subject number and visit, where applicable. All summaries will present the data by ARO-HBV dose level/cohort and overall (total subjects), as applicable.

Data collected during the main study (up to the Day 29 or Day 113 EOS visits) and at the additional follow-up visits (CHB cohorts only) will be presented in the same summary table, as appropriate. The first part of each table will present the main study results for the specific analysis. The second part of each table will include all data collected during the study, including data collected during the follow-up period, for the subset of CHB patients that consented to participate in the follow-up. All data will be included in the listings, and data collected during the follow-up period will be flagged in all event/medication-based listings. Separate figures that include all data will be presented for the subset of patients that participated in the follow-up period.

Unless otherwise stated, the following statistical approaches will be taken:

- Continuous variables: Descriptive statistics will include the number of non-missing values (N), mean, standard deviation (SD), median, minimum, maximum.
- Categorical variables: Descriptive statistics will include frequency counts and percentages per category. Percentages will be rounded to one decimal place, with the denominator being the number of subjects in the relevant population with non-missing data, unless otherwise specified.
- Imputation: No missing data will be imputed generally.
- Confidence intervals (CIs): CIs will be two-sided and will use 95% confidence levels unless specified otherwise.
- Baseline: Baseline values will be defined as the last non-missing observation (pre-dose value closest to the first dose) for each subject prior to the dosing of study medication (i.e. start of injection on Day 1).
- Repeat assessments (Safety): If there is a repeat test, the repeat result will be used in the analysis table and the original result will only be listed in the data listing.

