### **10.6.2 Biostatistical methods**

Descriptive statistics will be calculated for heart rate, PR interval, QRS interval, QT interval, and QTcF interval, including change from baseline (last pre-dose value on Day 1) for each dose level (cohort) for all time points assessed.

12-lead ECG measurements will be obtained at the scheduled time points after the participant is semi-supine for at least 3 minutes. Any abnormal ECGs will be repeated in triplicate, with each measurement approximately 1 minute apart. If triplicate ECG parameters are available, the average of the triplicate ECG parameters will be used. Unscheduled visits will be excluded from summary tables. However, the findings from the unscheduled will be listed.

In addition, the overall interpretation of 12-lead ECG results will be classified using frequency counts and percentages for the categories of Normal, Abnormal - Not Clinically Significant (NCS) and Abnormal - Clinically Significant (CS) for each treatment group for all time points assessed.

All ECG data will be presented in the by-subject data listings.

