14.3.3.14	Summary of Treatment Emergent Adverse Events Fitting the Definition of Local Injection Site Reactions (LISR) by System Organ Class and Preferred Term and by Severity	Safety	X
14.3.4.1	Laboratory – Hematology: Summary and Change from Baseline	Safety	X
14.3.4.2	Laboratory - Chemistry: Summary and Change from Baseline	Safety	X
14.3.4.3	Laboratory – Coagulation: Summary and Change from Baseline	Safety	X
14.3.4.4	Laboratory - Urinalysis: Summary and Change from Baseline	Safety	X
14.3.4.5	Summary of Haematology Shifts from Baseline	Safety	X
14.3.4.6	Summary of Biochemistry Shifts from Baseline	Safety	X
14.3.4.7	Summary of Coagulation Shifts from Baseline	Safety	X
14.3.4.8	Summary of Subjects with ALT above Upper Limit of Normal Over Time [CHB cohorts only]	Safety	X
14.3.5.1	Summary of Vital Signs	Safety	X
14.3.6.1	Summary of Physical Examination	Safety	X
14.3.7.1	Summary of ECG Values	Safety	X
14.3.7.2	Summary of ECG Findings	Safety	X

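### The planned laboratory tables cannot show ALT or AST worsening in CHB patients already above normal, and none counts patients reaching the protocol's own 3X and 10X levels

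*SAP*

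**What the plan says.** SAP 10.3.2 plans four outputs for ALT and AST:

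- descriptive statistics of the value and its change from baseline, by cohort and visit (Table 14.3.4.2);
- shifts made visit by visit, "Shift tables from Day 1 (pre-dose) to all follow-up visits will also be generated", with "values of Within Normal Limits (WNL), High, and Low used for the shift categories" (Table 14.3.4.6);
- one liver-specific count, "number of subjects with ALT above the upper limit of normal over time will be summarized for CHB cohorts", which is Table 14.3.4.8, "Summary of Subjects with ALT above Upper Limit of Normal Over Time";
- plots of means, and by-subject listings.

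SAP Section 3 adds a general rule: "Repeat assessments (Safety): If there is a repeat test, the repeat result will be used in the analysis table". It does not define a repeat.

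On entry, Protocol 7.3 excludes a CHB patient for "Hepatic transaminases (ALT or AST) > 5X ULN" at screening, so values above 1X and up to 5X ULN are eligible. Healthy volunteers must be at or below ULN at screening (Protocol 7.2).

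The protocol sets its own levels in two places. Section 6.3 uses ALT or AST above 3X ULN for volunteers. For CHB patients it uses ALT or AST above three times the Day 1 value, together with ALT above 10X ULN and a bilirubin or albumin change. Appendix 1 defines an ALT flare as more than three times baseline with ALT of 10X ULN or more. Both ask for confirmation by a repeat sample.

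**The concern.** A three-level shift has one open-ended High category. It can show that a normal patient became abnormal, but not that an abnormal patient became much worse. That matters here because many of the people studied have liver disease and some may start High. The ALT count has the same limit, since a patient above ULN on Day 1 is counted from the start.

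Three further gaps follow from the same design:

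- AST has no categorical summary beyond the shift table.
- For volunteers, whose protocol level is 3X ULN, a normal-to-High shift does not show whether that level was passed.
- Shifts are made to each visit separately, so they do not add up to a number of patients ever affected.

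The primary objective is safety and tolerability, measured by related adverse events. Protocol 4.7.1 names hepatic toxicity and ALT flares as risks and expects flares. Appendix 1 stresses the need to tell flares from drug injury. A reader of the study report would want to know how many patients per cohort reached the protocol's own levels, and no planned laboratory table gives that number.

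**Working it through.** The plan states no figure on this point, so there is none to reproduce. The check applies the SAP's classification to values in multiples of ULN and reads the table list.

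**1. Rise needed to reach the flare level.** For baseline b (X ULN), the level is L = max(3b, 10) and the fold rise is L/b. The range of b comes from the 5X screening limit; the 3X and 10X come from Appendix 1.

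| b | L (X ULN) | Fold rise | Shift cell | In ALT>ULN count |
|---|---|---|---|---|
| just above 1 | 10 | about 10 | High to High | before and after |
| 1.5 | 10 | 6.7 | High to High | before and after |
| 2 | 10 | 5.0 | High to High | before and after |
| 3 | 10 | 3.3 | High to High | before and after |
| 3.33 | 10 | 3.0 | High to High | before and after |
| 4 | 12 | 3.0 | High to High | before and after |
| 5 | 15 | 3.0 | High to High | before and after |

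A move from 1.2X to 1.3X ULN falls in the same cell as a move from 1.2X to 10.5X.

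**2. Whole-cohort example (assumed values; the documents give no ALT data).** Take a cohort of 8 with 4 patients at 2X ULN and 4 at 0.7X. In case A nothing changes. In case B the four High patients reach 12X ULN, which is 12/2 = 6 times baseline.

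- Shift table: 4 High-to-High and 4 WNL-to-WNL in both cases.
- ALT>ULN count: 4 in both cases.
- Patients above 3X baseline and above 10X ULN: 0 in A, 4 in B.

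The planned tables were also identical between A and B for cohorts of 4 and 12, with one, half or all patients High at baseline.

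**3. Volunteers.** From a normal Day 1 value, 1.1X and 3.5X ULN are both WNL-to-High. Only the second passes 3X ULN.

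**4. Patients versus visits.** Protocol Table 1.2 has post-dose laboratory visits on Days 2, 8, 15, 29, 43, 57, 71, 85 and 113, which is 9. Table 1.5 adds Days 169, 225, 281, 337 and 393, giving 9 + 5 = 14. Cohort 12 stops at Day 337, giving 9 + 4 = 13. Suppose one WNL-to-High patient appears at each of three visits in a cohort of 4. That fits anything from 1 patient ever High (1/4 = 25%) to 3 patients (3/4 = 75%).

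**5. Table list.** Of the eight laboratory tables, 14.3.4.1 to 14.3.4.8, none uses a multiple of ULN or of baseline.

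**6. Weight of one patient.** 1/4 = 25% of a volunteer active arm; 1/8 = 12.5% to 1/4 = 25% of a CHB cohort of 4 to 8; 1/12 = 8.3% of Cohort 12.

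**The case against.** The best defence is that other outputs carry the information. Table 14.3.4.2 gives the maximum ALT and AST, and the change from baseline, at each visit. Baseline ALT is summarised for CHB cohorts (SAP 7.1). Every value is listed, and with cohorts of 4 to 12 the patients could be counted by hand. Worsening that the investigator judges clinically significant becomes an adverse event (Protocol 10.2). If a patient meets a stopping criterion and is not discontinued, the reason goes into the safety committee minutes (Protocol 6.3). The primary objective concerns related adverse events, not laboratory thresholds. The 3X and 10X levels serve case-by-case decisions and monitoring.

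Much of this stands. A reader might infer that ALT worsening would be invisible in the report, and that is not so. Still, maxima are in laboratory units and give neither the ratio to ULN or to that patient's baseline, nor a number of patients. Adverse-event capture rests on judgement, and intensity is graded by effect on daily activities (Protocol 10.5.1), so a symptom-free rise has no laboratory grade. Counting by hand at the maximum CHB enrolment means reading 84 x 9 = 756 ALT values to Day 113. Committee minutes are not a planned report table.

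Three stronger readings are tempting but unsupported:

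- That the SAP breaks a protocol commitment. The Protocol synopsis (Data Analysis) promises descriptive statistics and shift tables for laboratory abnormalities, and the SAP delivers both.
- That the repeat rule, or the exclusion of unscheduled visits, hides peaks. The protocol's levels themselves require confirmation on repeat, and the sentence "Unscheduled visits will be excluded from summary tables" stands in the ECG section only. The laboratory section says nothing on unscheduled samples, and no document allows the effect to be sized.
- That reporting the laboratory's HP flag as H discards a severity grade. The SAP does not define HP, and the values stay in the listings.

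**Conclusion.** The point holds as a gap in reporting. For any CHB patient High at baseline, the shift table and the ALT count give the same result whether ALT stays flat or passes both 3X baseline and 10X ULN. No laboratory table counts patients at the protocol's own levels, in CHB patients or in volunteers.

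The number of patients affected cannot be computed. The documents do not give the baseline ALT distribution, and the 5X limit applies at screening, so Day 1 values may differ. The cohort of 8 and the 25% to 75% range illustrate the limit of the tables and do not predict results. The gap is worth closing because it costs little and concerns named liver risks. It does not threaten the trial's conclusions or depart from what the protocol promised.

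**What to change.** Add one table for each population: volunteers, CHB patients to Day 113, and the CHB follow-up subset. By cohort, count patients whose worst post-baseline ALT or AST reaches the levels the protocol already names:

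- volunteers: above 3X ULN;
- CHB patients: above 3X the Day 1 baseline; 10X ULN (ALT); and both together.

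State that these tables use all samples, including originals, repeats and unscheduled draws. Show initial results and results confirmed on repeat in separate columns. The existing shift tables can stay as they are.

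Section 6.3 requires ALT above 10X ULN, while Appendix 1 accepts a value of exactly 10X. The sponsor must reconcile the two passages before programming; this review takes no view on which is right.

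The cost is SAP wording and one extra table per population, from data already collected. The counts will include unconfirmed values and natural CHB fluctuation, and the CHB cohorts have no placebo arm. A footnote should say that the counts describe rises and do not attribute them to drug.

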## **10.4 Vital Signs**

### **10.4.1 Definition of variables**

- Systolic Blood Pressure (SBP) (mmHg)
- Diastolic Blood Pressure (DBP) (mmHg)
- Pulse Rate (beats/min)
- Body Temperature (°C)
- Respiratory rate (breaths/minute)

### **10.4.2 Biostatistical methods**

All vital sign parameters will be summarized using descriptive statistics for each dose level (cohort) for all time points assessed, including change from baseline (last pre-dose value) for all post-dose assessments. Pre-dosing vital signs on Day 1 will be used as baseline data. If the baseline value is missing, then the data from screening will be used as baseline data as appropriate.

All vital sign parameters will be listed for each dose level (cohort) for all time points assessed.

## **10.5 Physical examination**

### **10.5.1 Definition of variables**

The following body systems will be assessed:

- General Appearance
- HEENT (Head, Eyes, Ears, Nose and Throat)
- Cardiovascular
- Lungs
- Abdomen
- Lymph nodes
- Genitourinary
- Extremities
- Neurological
- Skin
- Musculoskeletal
- Other

For abnormal result of physical examination:

- Abnormal NCS (Not Clinically Significant)
- Abnormal CS (Clinically Significant).

### **10.5.2 Biostatistical methods**

Physical examination will be summarized by study visit and treatment cohort. The frequency counts and percentages of subjects with different physical examination results and their clinical significance (for abnormal) will be summarized.

According to the schedule of assessment, a complete physical exam will be performed at Screening. Symptom-directed physical examinations will only be conducted at other visits as necessary. Only complete exams (screening) will be summarized.

By-subject data listings will be generated for all the physical examination data, including the Investigator assessment of clinical significance for abnormal findings, for all time points assessed.

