Blood samples will be collected from each NHV (Cohorts 1-5) participant during the study for Complement analysis after dose 1 (all cohorts). Two blood samples will be collected at each collection time. One sample will be processed to produce serum for complement CH50 analysis, and one sample will be processed to produce plasma, which will be analyzed to determine the level of split products Bb, C5a, C4a, and C3a. Initially the 0 (pre-) and 2-hour post-dose samples will be analyzed, with the remaining samples analyzed only if a change from pre-dose baseline is observed at 2 hours.

Excretion and Metabolism:

Seven blood samples will be collected from each subject for metabolic analysis after dose 1 (Cohorts 2-5) per the Schedule of Assessments. Samples will be frozen at -80°C for analysis outside of this study.

Urine collections will be performed after dosing per the Schedule of Assessments.

Data Analysis:

Two separate data analyses will be performed, one for all subjects through EOS (Day 29 for NHVs and Day 113 for CHB patients), and one additional and separate analysis for CHB patients who consent to the additional follow up through Day 337 (Cohort 12 only) or Day 393. Separate analyses including and excluding Cohort 12 may also be completed.

Screening, Compliance, Tolerability and Safety Data:

In general, safety analyses will be performed and the results summarized by cohort. Post-treatment safety assessments will be compared with measurements recorded at baseline. Treatment emergent AEs will be summarized using the latest version of the Medical Dictionary for Regulatory Activities (MedDRA) by System Organ Class (SOC) and Preferred Term (PT). The incidence and frequency of AEs, SAEs, related AEs, related SAEs, and AEs leading to discontinuation, will be summarized by cohort per SOC, PT, and severity. All Adverse Events will also be presented in listings. The duration of AEs will be determined and included in listings, along with the action taken and outcome. The incidence of laboratory abnormalities will be assessed using descriptive summary statistics and shift tables. Vital sign measurements will be summarized at each scheduled time point using descriptive statistics. Abnormal physical examination findings will be summarized by time point and presented in subject listings. ECG parameters, changes from baseline, and qualitative assessments will be summarized. Pregnancy and FSH test results will be listed separately by time point.

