* Repeat if > 2 weeks from Screening

1. Symptom-directed PEs to be performed by visit as necessary.

2. ECGs: Measured pre-dose and at 1 and 2 hours post-dose; more frequently per hour if necessary. Performed prior to other invasive procedures.

3. PK: (plasma) Blood samples collected 0 (pre-dose), 15 min, 0.5, 1, 2, 3, 6, 24 & 48 hours post-dose

4. Cytokines Panel A only in NHVs): (whole blood). Serial venous blood samples collected 0 (pre-dose) 0.5, 2, 6, & 24 hours after dosing.

5. Complement: (serum and plasma). 2 venous blood samples collected 0 (pre-dose), 0.5, 2, 6 & 24 hours after dosing.

6. Vitals: Measured pre-dose and at 5 min, 0.5, 1, 2, 3, and 6 hours post-dose.

7. Meals: Lunch, Dinner, and snack on Day 1 at approximately 2 hours, 6 hours and 8 hours post-dose. Breakfast optional on Day

8. Urine pregnancy test for females of childbearing potential only.

9. AE/SAE data capture begins from time of informed consent.

10. Clinical Chemistry, Hematology, Coagulation and Urinalysis pre-dose and at 6 hours post-dose.

11. Performed for females not of childbearing potential to confirm postmenopausal status

12. Pre-dose

13. Cohorts 2-5 only Metabolite ID: Blood samples collected 0 (pre-dose), 0.5, 1, 3, 6, 24 & 48 hours post-dose

14. **Cohorts 2-5 only:** Collect spot urine samples on days 1 (pre-dose), 8, 15, and 29 and aliquot into 3 aliquots and freeze and store at -80C. Collect all urine from 0-6 hours and 6-24 hours after dosing. Aliquot each collection into three aliquots and freeze and store at -80C. Discard the remainder of the collected urine.

Table 1.2: Cohorts 1b, 1c, 2b, 3b, 4b, 5b, 8 and 9 (CHB patients, three Q28 day doses)

Assessment	Screen (Days -60 to -1)		Day 1	Day 2	Day 8	Day 15 (± 2)	Day 29, 57 (± 2)	Day 43, 71 (± 2)	Day 85 (± 2)	Day 113 (± 2) EOS	Early Termination
Informed Consent	X	RANDOMIZE									
Eligibility Criteria	X		X ⁹								
Body Mass Index	X										
Demographics	X										
Medical History	X		X*								
Drug Screen	X										
Hepatitis/HIV Serology Screen	X										
Physical Exam ¹	X		X*	X ¹	X ¹	X ¹	X ¹	X ¹	X ¹	X	X ¹
FSH	X ⁸										
Pregnancy test	X ⁵		X ⁵				X ⁵			X	X
ECG	X		X ²				X ²			X	X
Vital Signs (BP, temp, RR, heart rate)	X		X ⁴	X	X	X	X ⁴	X	X	X	X
Hepatic Fibrosis Measure (FibroScan®)	X										
Clinical Labs (heme, coag, chem, UA)	X		X ⁷	X	X	X	X ⁷	X	X	X	X
HBeAg qualitative	X										
Quantitative HBsAg, HBcrAg, HBeAg (e+ only) HBV DNA, HBV RNA	X		X		X	X	X	X	X	X	X

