Documentation of the participant's fulfillment of the entry criteria, for all participants considered for the study and subsequently included or excluded, is to be completed by the PI, or medically qualified designee. Documentation of screening failure details will be recorded using eligibility screening forms or a participant screen failure log. Procedures outlined in the Schedule of Assessments will be performed. Meals and water will be provided while participants are confined at the clinical facility. Timing will abide by fasting restrictions outlined in Section 7.5.

9.3.2 *Demographics/Medical History*

Medical History will include medication use over the previous 30 days, including vitamins, over-the-counter, prescription drugs, recreational drugs or supplements and alcohol and tobacco use.

9.3.3 *Physical Exam*

A complete physical exam will be performed at Screening and as per Schedule of Assessments.

At Screening, height (centimetres, without shoes) and weight (kilograms, without shoes) will be obtained to determine BMI.

At all other time points outlined in the Schedule of Assessments, a symptom-directed physical exam will be performed if indicated.

9.3.4 *Electrocardiogram*

A single 12-lead ECG measurement will be obtained at time points outlined in the Schedule of Assessments after the participant is supine for at least 3 minutes. Any abnormal ECGs will be repeated in triplicate, with each measurement approximately 1 minute apart. ECGs will be performed prior to venipuncture and other invasive procedures.

9.3.5 *Vital Sign Assessments*

Systolic/diastolic blood pressure, temperature, heart rate, respiratory rate (breaths/min) will be obtained at time points outlined in the Schedule of Assessments after the participant is seated or semi-supine for at least 3 minutes. Vitals signs will be obtained prior to venipuncture and other invasive procedures.

9.3.6 *Clinical Laboratory Tests & Pharmacodynamic Values*

Blood and urine samples will be collected to perform clinical laboratory tests run at a central laboratory. Participants will be required to fast for the Screening sample collections.

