11 DATA ANALYSIS AND STATISTICAL CONSIDERATIONS

11.1 *Data analysis through EOS and Additional follow-up*

Two separate data analyses will be performed, one for all subjects through EOS (Day 29 for NHVs and Day 113 for CHB patients), and one additional and separate analysis for CHB patients who consent to the additional follow up.

11.2 *Sample Size Considerations*

This study represents a proof of principle study, and as such no formal sample size calculation was performed. Results from this study will be utilized in sample size calculations for subsequent studies.

11.3 *Screening Data*

Demographics will be tabulated by participant and summarized by cohort and treatment group. Eligibility assessments at baseline, including medical/surgical history data and physical examination data (including height and weight), will be listed for each participant.

11.4 *Safety/Tolerability Data*

In general, safety analyses will be performed and the results summarized by-cohort and treatment group.

Treatment-emergent AEs will be summarized using the latest version of MedDRA by System Organ Class (SOC) and Preferred Term (PT), classified from verbatim terms. The incidence and percentage of participants with at least 1 occurrence of a PT will be included, per the most severe grade using a 3-point scale (mild, moderate, severe). The number of events per Preferred Term will also be summarized. Causality (relationship to study treatment) will be summarized separately.

The incidence and frequency of AEs, SAEs, related AEs, related SAEs and AEs leading to withdrawal, dose modification, or treatment discontinuation will be summarized by dose and treatment group per SOC and Preferred Terms. AEs will also be summarized in listings. The duration of AEs will be determined and included in listings, along with the action taken and outcome.

The incidence of laboratory abnormalities will be summarized. Results for variables that are not coded will be presented in the listings as “below, within, and above” the normal limits of the laboratory. Pregnancy test results will be summarized separately by time point.

Vital sign measurements will be summarized at each scheduled time point using descriptive statistics. Physical examination findings will be summarized by time point and presented in subject listings.

ECG parameter changes overall, changes from baseline and qualitative assessments will be summarized.

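### SAP 10.5.2 limits the physical-examination summary table to Screening, leaving out the end-of-study examination that the schedule appears to mark as complete for most cohorts

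*SAP*

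**What the plan says.** SAP 2.3 and protocol 9.7 both list physical examinations among the safety endpoints.

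SAP 10.5.2 makes four statements that bear on this point:

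- It opens with "Physical examination will be summarized by study visit and treatment cohort".
- Citing the schedule, it places the complete examination at Screening and says of the rest: "Symptom-directed physical examinations will only be conducted at other visits as necessary".
- It draws the rule: "Only complete exams (screening) will be summarized". The output concerned is Table 14.3.6.1.
- It closes with "By-subject data listings will be generated for all the physical examination data", covering all time points and including the investigator's rating of clinical significance (Listing 16.2.10.1).

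The protocol's analysis text is wider. The synopsis (Data Analysis) says "Abnormal physical examination findings will be summarized by time point and presented in subject listings", and section 11.4 says "Physical examination findings will be summarized by time point and presented in subject listings".

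On conduct, protocol 9.3.3 says "A complete physical exam will be performed at Screening and as per Schedule of Assessments". It then adds that all other scheduled time points have a symptom-directed examination if indicated. In the schedule tables, footnote 1 reads "Symptom-directed PEs to be performed by visit as necessary".

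**The concern.** Within one short section the SAP promises a summary by visit and then restricts it to a single pre-treatment visit. The only reason it gives is its reading of the schedule, and the schedule seems to show a second complete examination, after dosing, for most cohorts.

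Safety and tolerability are the primary objective. A physical-examination table built from Screening alone describes participants before any study drug, so it cannot show a difference between doses or between active and placebo volunteers. SAP section 10 also asks for safety endpoints to be analysed separately for the main study and for the whole study including follow-up. For this endpoint's table, both analyses would contain the same pre-dose data. Vital signs and ECG, by contrast, are summarised at all time points assessed (SAP 10.4.2 and 10.6.2).

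What is most directly lost is any tabulation of post-dose abnormalities rated not clinically significant, a category that SAP 10.5.1 defines.

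**Working it through.** No power or alpha calculation is involved. The check is a cell-by-cell reading of the physical-examination row in protocol Tables 1.1 to 1.6, followed by a count of the participants affected.

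**Step 1: the schedule.**

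| Table | Cohorts | Screening | Intermediate visits | End of study |
|---|---|---|---|---|
| 1.1 | 1 to 5 (volunteers) | X | X¹ | X (Day 29) |
| 1.2 | 1b, 1c, 2b to 5b, 8, 9 | X | X¹ | X (Day 113) |
| 1.6 | 12 | X | X¹ | X (Day 113) |
| 1.3 | 6 | X | X¹ | X¹ (Day 113) |
| 1.4 | 7, 10, 11 | X | X¹ | X¹ (Day 113) |
| 1.5 | follow-up, CHB | n/a | X¹ at every visit | n/a |

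Tables 1.1 to 1.4 and 1.6 also have an X* just before dosing (Day -1 for volunteers, Day 1 for patients), meaning a repeat if more than 2 weeks have passed since Screening. Early termination is X¹ throughout.

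**Step 2: what a plain X means.** No table defines it. Two things support reading it as a complete examination. First, protocol 9.3.3 expects complete examinations at Screening and wherever the schedule calls for them, which is wider than Screening alone. Second, the sponsor sets the superscript cell by cell. The Version 2.0 summary of changes describes adding a symptom-directed examination at Day 113 for Cohort 7, and current Table 1.4 shows that cell as X¹. An unmarked X at the same visit in Tables 1.1, 1.2 and 1.6 therefore denotes something else, and it matches the mark used at Screening.

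**Step 3: reproduce the planned totals.** Cohort sizes are from SAP 2.4. The six escalation cohorts have 4 to 8 patients each. Cohorts 6 to 11 are taken at their maximum of 4, and Cohort 12 has 12.

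- CHB minimum: 6×4 + 6×4 + 12 = 60
- CHB maximum: 6×8 + 6×4 + 12 = 84
- Volunteers: 5×6 = 30

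These match the SAP's 60, 84 and approximately 30. (Protocol 7.1 prints a minimum of 50, which the cohort sizes do not give.)

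**Step 4: participants with a plain X at end of study.** This removes Cohorts 6, 7, 10 and 11.

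- Cohorts: 5 + 13 = 18 in all; 18 − 4 = 14
- CHB minimum: 6×4 + 2×4 + 12 = 44 of 60 (73%)
- CHB maximum: 6×8 + 2×4 + 12 = 68 of 84 (81%)
- All participants, minimum: 30 + 44 = 74 of 90 (82%)
- All participants, maximum: 30 + 68 = 98 of 114 (86%)

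**Step 5: post-dose visits in each output as the SAP stands.** Table 14.3.6.1 has none. Listing 16.2.10.1 has every visit at which an examination was done.

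**The case against.** The strongest reply is that the SAP may have read the schedule correctly. The row label itself carries footnote 1 in all six tables, so the note could govern the whole row. Screening is the only time point that protocol 9.3.3 names for a complete examination, and its closing sentence makes the remaining time points symptom-directed. No reason is given why the Q28-day cohorts should have a complete end-of-study examination when Cohorts 6, 7, 10 and 11 do not. This has some force: the plain X is an inference, though a well-supported one. It does not remove the conflict, because a Screening-only table fails the commitment to summarise by time point, and the SAP's own first sentence, however the X is read.

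The second reply concerns consequence, and most of it stands. A reader might infer that the endpoint contains no post-dose data at all, or that a safety signal would be hidden. The documents do not support either. The listings carry all time points. Under protocol 10.2, abnormal assessments that are clinically significant or have clinical sequelae are recorded as adverse events, so they reach the treatment-emergent tables by cohort and, for volunteers, against pooled placebo. SAP 2.4 also says the small cohorts are not meant for inference.

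A reader might likewise infer that every cohort has a complete end-of-study examination. Cohorts 6, 7, 10 and 11, up to 16 patients, do not.

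Lastly, it is reasonable to keep symptom-directed examinations out of summary tables. They are done only when needed, so a percentage based on them has no clear denominator.

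**Conclusion.** Wrong as written, minor in severity. The Screening-only rule contradicts the sentence that opens SAP 10.5.2, protocol 11.4 and the synopsis, and its stated premise conflicts with Tables 1.1, 1.2 and 1.6. As it stands, the only summary table for a named safety endpoint has no post-dose visit. Post-dose findings reach the listings, and reach the adverse-event tables if clinically significant; those rated not clinically significant reach no table.

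The scheduled end-of-study examination is omitted for 14 of 18 cohorts, which is 74 of 90 to 98 of 114 planned participants. That count assumes that a plain X is a complete examination and that Cohorts 6 to 11 fill to 4 each. The internal contradiction depends on neither assumption.

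**What to change.** In SAP 10.5.2:

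- Delete the bracketed word and state that every scheduled complete examination is summarised by visit and cohort as normal, abnormal NCS or abnormal CS. This includes Day 29 for volunteers and Day 113 for Cohorts 1b, 1c, 2b to 5b, 8, 9 and 12.
- Correct the sentence that places the complete examination only at Screening.
- Preferably add a shift from the last pre-dose complete examination to end of study. This goes beyond the by-time-point summary that the protocol promises.
- Keep symptom-directed examinations in listings, including those at end of study for Cohorts 6, 7, 10 and 11.

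If the sponsor confirms that the plain X was not meant as a complete examination, the SAP should say so and record the departure from protocol 11.4 with a reason.

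The cost is a change of SAP wording, added visits in one table and, if wanted, one shift table. No new data collection is needed.
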